6.5 Replacement of individual subjects after withdrawal

N/A

6.6 Follow-up of subjects withdrawn from treatment

N/A

6.7 Premature termination of the study

N/A

7. SAFETY REPORTING

7.1 Temporary halt for reasons of subject safety

N/A

7.2 AEs, SAEs and SUSARs

7.2.1 Adverse events (AEs)

Adverse events are defined as any undesirable experience occurring to a subject during the study, whether or not considered related to esketamine treatment. All adverse events reported spontaneously by the subject or observed by the investigator or his staff will be recorded.

7.2.2 Serious adverse events (SAEs)

A serious adverse event is any untoward medical occurrence or effect that

- results in death;
- is life threatening (at the time of the event);
- requires hospitalisation or prolongation of existing inpatients' hospitalisation;
- results in persistent or significant disability or incapacity;
- is a congenital anomaly or birth defect; or
- any other important medical event that did not result in any of the outcomes listed above due to medical or surgical intervention but could have been based upon appropriate judgement by the investigator.

An elective hospital admission will not be considered as a serious adverse event.

The investigator will report all SAEs to the manufacturer and Lareb without undue delay after obtaining knowledge of the events.

7.2.3 Suspected unexpected serious adverse reactions (SUSARs)

Adverse reactions are all untoward and unintended responses to an investigational product related to any dose administered.

Unexpected adverse reactions are SUSARs if the following three conditions are met:

1. the event must be serious (see chapter 9.2.2);
2. there must be a certain degree of probability that the event is a harmful and an undesirable reaction to the medicinal product under investigation, regardless of the administered dose;

3. the adverse reaction must be unexpected, that is to say, the nature and severity of the adverse reaction are not in agreement with the product information as recorded in:
 - Summary of Product Characteristics (SPC) for an authorised medicinal product;

The sponsor will report expedited the following SUSARs through the web portal

ToetsingOnline to the METC *<reporting via webportal ToetsingOnline is only applicable for investigator initiated studies>*:

- SUSARs that have arisen in the clinical trial that was assessed by the METC;
- SUSARs that have arisen in other clinical trials of the same sponsor and with the same medicinal product, and that could have consequences for the safety of the subjects involved in the clinical trial that was assessed by the METC.

The remaining SUSARs are recorded in an overview list (line-listing) that will be submitted once every half year to the METC. This line-listing provides an overview of all SUSARs from the study medicine, accompanied by a brief report highlighting the main points of concern.

The expedited reporting of SUSARs through the web portal Eudravigilance or ToetsingOnline is sufficient as notification to the competent authority.

The sponsor will report expedited all SUSARs to the competent authorities in other Member States, according to the requirements of the Member States.

The expedited reporting will occur not later than 15 days after the sponsor has first knowledge of the adverse reactions. For fatal or life threatening cases the term will be maximal 7 days for a preliminary report with another 8 days for completion of the report.

7.3 Annual safety report

N/A

7.4 Follow-up of adverse events

All AEs will be followed until they have abated, or until a stable situation has been reached. Depending on the event, follow up may require additional tests or medical procedures as indicated, and/or referral to the general physician or a medical specialist.

SAEs need to be reported till end of study within the Netherlands, as defined in the protocol

7.5 [Data Safety Monitoring Board (DSMB) / Safety Committee]

N/A

8. STATISTICAL ANALYSIS

8.1 Primary study parameter(s)

For the continuous MADRS-scores differences relative to baseline will be used over time. This will initially be done for the full sample.

Subsequently we will investigate the association of the primary outcome with the level of treatment resistance and specific aspects thereof (e.g. ECT-non-responders) with linear mixed models (to accommodate repeated follow-up measurements and unavoidable missing data over time).

For the second aim of the project, we aim to pool this data across different treatment centres in order to increase power and obtain more quantitative information about possible characteristics of responders vs non-responders.

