6. METHODS

6.1 Study parameters/endpoints

6.1.1 Main study parameter/endpoint

Primary endpoint is the change (relative to baseline) in clinician-rated MADRS score (Montgomery 1979) at 4 and 8 weeks.

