6.3 Study procedures

All procedures are part of routine clinical practice. No invasive or additional measurements will be done.

Initial assessment for eligibility for esketamine intranasal treatment consists of:

- Assessment of in- and exclusion criteria including determination of DSM-5 diagnosis by either clinical or semi-structured clinical interview.
- Level of treatment resistance (DM-TRD)
- Drug and alcohol screening (if appropriate)
- Pregnancy test (if appropriate)
- Routine ECG and laboratory assessment
- Assessment of baseline MADRS and IDS-SR score

- Internet-based delivery of PIT test via GDPR certified online testing platform Gorilla

After inclusion, patients will continue the antidepressant they are currently using. This treatment might be optimized according to dosing or TDM. Patients start treatment in accordance with the schedule provided by the manufacturer and described under 4.1 (Figure 1).

Every session:

- VAS-ratings of mood will be asked at every session before-after esketamine administration
- Adverse effects including dissociation at 40 minutes after the last dose of esketamine, or – in case of more pronounced dissociation- as close as possible and at the end of the session (KSET)

During the Induction Phase weekly assessments of effectiveness will be done. In the Continuation (maintenance) Phase this will be continued every second week at frequencies of administration $\geq 1/\text{week}$, while if the frequency is $\leq 1/2 \text{ weeks}$, assessments will be done monthly for the first 2 months, followed by every two months thereafter:

- Repeated assessments of MADRS and IDS-SR scores.

Formal evaluations of the treatment will be performed at regular intervals according to clinical judgement. The first evaluation of effectiveness will be after 4 weeks of twice weekly administration. This will also be the second and last time that the subject is asked to do the online PIT test.

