6.4.1 Specific criteria for withdrawal

- Intolerance of esketamine intranasal treatment
- Non-response to the treatment after 4 weeks

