8.2 Secondary study parameter(s)

For secondary outcome study parameters (IDS-SR, QoL and level of functioning) we will use a comparable approach as for the primary study outcome.

Discontinuation rates will be described over time, also in relation with level of TRD.

Occurrence of dissociative symptoms and blood-pressure per session will be examined for stability over time. Moreover, the severity of these adverse effects and the variation thereof between patients will be described descriptively.

For the second aim of the project, we aim to pool this data across different treatment centres in order to increase power and obtain more quantitative information about possible characteristics of responders vs non-responders.

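### Section 8.1 attaches the plan's only missing-data method to the association analysis and not to the full-sample MADRS result; read as written, the week-8 change rests mainly on responders and is too favourable

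*Protocol*

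**What the plan says.** Protocol 6.1.1 sets two primary time points: "Primary endpoint is the change (relative to baseline) in clinician-rated MADRS score (Montgomery 1979) at 4 and 8 weeks". Section 8.1 then describes two steps.

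- Step 1, full sample: "For the continuous MADRS-scores differences relative to baseline will be used over time. This will initially be done for the full sample". No model, estimator or missing-data rule is named.
- Step 2: "Subsequently we will investigate the association of the primary outcome with the level of treatment resistance and specific aspects thereof". This step is to be done "with linear mixed models (to accommodate repeated follow-up measurements and unavoidable missing data over time".

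That parenthesis is the only place where the protocol says how missing data are handled. For IDS-SR, quality of life and functioning, 8.2 says "we will use a comparable approach as for the primary study outcome".

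Other sections decide who still has a score at week 8:

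- 6.4.1 lists two withdrawal criteria. One is intolerance; the other is "Non-response to the treatment after 4 weeks".
- The Summary (Intervention) has treatment responders enter the Continuation Phase.
- 6.3: "During the Induction Phase weekly assessments of effectiveness will be done". After induction, the rating schedule depends on how often the drug is given.
- 6.6, on follow-up of patients withdrawn from treatment, is marked not applicable.

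**The concern.** The protocol expects missing scores, names a method to accommodate them, and attaches it to the association question. The same gaps affect the full-sample effectiveness result, which is the first figure a reader will look for. A difference from baseline at week 8 exists only for a patient rated at week 8. If step 1 is carried out as worded, patients withdrawn at week 4 for non-response drop out of the week-8 figure because they did badly. The result then describes change among those still being treated, whereas the primary objective concerns the treated population. The weekly induction ratings carry information on who left, and a simple difference score makes no use of them. The wording in 8.2 passes the same approach on to the main secondary scales.

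**Working it through.** **No figure to reproduce.** Section 2.4 reports no power calculation, and the protocol gives no mean change, SD, response rate or dropout. All inputs below are assumptions.

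**Week 8, closed form.** Assume baseline MADRS B ~ N(32, 6²); change at weeks 4 and 8 independent of B, with SD 10 and mean −m (m = 8, 12 or 16) at both visits; correlation r between the two changes of 0.5, 0.7 or 0.85; non-response = less than 50% reduction at week 4. Loss to intolerance is taken as unrelated to outcome here, so it does not affect the bias.

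- A responder has C4 + 0.5·B ≤ 0. This sum has mean 16 − m and SD √(100 + 9) = 10.44.
- Responder share: p = Φ(a), with a = (m − 16)/10.44.
- Responders exceed the full-sample week-4 improvement by D = (100/10.44)·φ(a)/p.
- If all non-responders leave, the overstatement at week 8 is r·D.
- If a share q of them leaves, it is r·D·p·q / (1 − q(1 − p)).

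Worked case, m = 12 and r = 0.7: a = −0.383, p = 0.351, φ(a)/p = 1.057, D = 9.578 × 1.057 = 10.12. The overstatement is 0.7 × 10.12 = 7.1 points, an observed mean of about −19.1 against a true −12.0.

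| m | p | D | r = 0.5 | r = 0.7 | r = 0.85 |
|---|---|---|---|---|---|
| 8 | 0.22 | 12.85 | 6.4 | 9.0 | 10.9 |
| 12 | 0.35 | 10.12 | 5.1 | 7.1 | 8.6 |
| 16 | 0.50 | 7.64 | 3.8 | 5.3 | 6.5 |

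(Overstatement in MADRS points if all leave.) A simulation of 400,000 patients per cell gave 3.8 to 11.0.

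**Fewer non-responders leave** (m = 12, r = 0.7):

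- q = 0.25: 7.09 × 0.351 × 0.25 / (1 − 0.25 × 0.649) = 0.7
- q = 0.50: 1.8
- q = 0.75: 3.6

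Over all nine combinations of m and r, q = 0.25 gives 0.4 to 0.9 and q = 0.50 gives 1.2 to 2.2.

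**Other threshold.** If instead everyone below a 25% reduction leaves, the same formulae (0.25 in place of 0.5) give 1.8 to 6.7.

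**Second set of assumptions.** Simulation with n = 350, true change −10, −14 or −18, score SD 11, 4-week correlation 0.5 or 0.7, about 13% stopping after week 2, and everyone below 50% reduction leaving at week 4. Observed week-8 means were −14.7 to −15.5, −17.6 to −18.2 and −20.6 to −21.0, an overstatement of 2.6 to 5.5 points.

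**Week 4.** Early loss of 5%, 10% or 15% for intolerance, with log-odds of leaving of −0.7, 0 or +0.7 per SD of worse week-4 outcome, gives a bias between −1.1 and +1.1 points. The sign follows the assumed link between intolerance and outcome, which the protocol does not state.

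**Does a mixed model help?** In the first set-up, an estimate conditioning on baseline and week 4 returned −11.9 to −12.0 against a true −12.0. In the second, an unstructured repeated-measures model gave −9.5, −14.2 and −17.8 to −18.1 against −10, −14 and −18. A random-intercept-only model on baseline, week 4 and week 8 (n = 350, m = 12, r = 0.7) gave −16.6 against −11.9, so it removed only part of the bias.

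**The case against.** A reader might infer that the protocol prescribes a raw or complete-case mean. It does not. Section 8.1 names no estimator, its wording partly restates the endpoint, and a change score can itself be the outcome of a mixed model. Further detail may sit in a statistical analysis plan or in the pre-registered plans promised in 8.3. This stands: the point concerns what the text yields if followed as written. It remains a point because the protocol is not silent. It names a remedy and attaches it to the later step.

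A reader might also take both primary time points to be too favourable. That holds for week 8 and later only. Before week 4 the listed criterion that applies is intolerance, and nothing in the protocol links intolerance to MADRS outcome.

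The upper figures assume that every patient below a 50% reduction leaves. The protocol sets no such threshold, and 3.1 bases continuation on the clinician's evaluation of symptoms, functioning or quality of life. This stands, and is why the partial-withdrawal figures belong beside the full ones.

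The simulated remedy is favoured by construction: leaving depends only on recorded MADRS. Under 3.1 it may depend on other things too. The target, week-8 change had treatment continued, is also hypothetical for patients taken off treatment. Both stand, and call for a stated target and a sensitivity analysis.

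It is tempting to add that the two steps will produce conflicting effectiveness figures. Nothing says that marginal means from the association model will be reported, so that is not supported.

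Finally, observed change with the number rated is a legitimate summary for a descriptive cohort. It should stay, labelled as such.

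**Conclusion.** The point holds for week 8 and the later 4-weekly MADRS changes. The full-sample result is described only as differences to baseline, while the plan's one missing-data method serves the later association step. Given withdrawal for non-response, ratings tied to dosing and no follow-up after withdrawal, a result produced as written would rest mainly on responders and overstate improvement.

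The direction requires that at least some non-responders leave and that week-4 and week-8 changes are positively correlated. The size is illustrative only: about 1 to 2 points if a quarter to a half of week-4 non-responders leave, and roughly 3 to 11 points if all those below 50% reduction leave. At week 4 the bias is within about 1 point, of undetermined sign. A mixed model cures this only if it uses the induction ratings with an adequate covariance structure and leaving is explained by the recorded scores. This is an inexpensive improvement that the sponsor should make; it is not evidence that a wrong estimator has been fixed.

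**What to change.** In 8.1:

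- State that full-sample changes at weeks 4 and 8 are estimated from a repeated-measures linear mixed model. Include every patient with a baseline rating and all MADRS ratings (baseline, weekly induction, continuation), with categorical time and an unstructured or similarly flexible within-patient covariance, not a random intercept alone. Report 95% confidence intervals.
- State that, under missing at random, this describes change as if treatment had continued.
- Add a sensitivity analysis for patients withdrawn at week 4.
- Keep observed differences as a labelled descriptive summary, with the number rated at each visit.

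In 8.2, apply the same to IDS-SR. For EQ-5D-5L and WHODAS-2.0, use the available 4-weekly scores (6.1.2) and note that fewer ratings are available to explain who left, because the repeated ratings in 6.3 cover only MADRS and IDS-SR.

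Cost: a few sentences in 8.1 and 8.2 and in the pre-registered plan, with no new visits, data or patients. The downsides are a less favourable week-8 figure and reliance on leaving being explained by the recorded scores.

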8.2 Secondary study parameter(s)

For secondary outcome study parameters (IDS-SR, QoL and level of functioning) we will use a comparable approach as for the primary study outcome.

Discontinuation rates will be described over time, also in relation with level of TRD.

Occurrence of dissociative symptoms and blood-pressure per session will be examined for stability over time. Moreover, the severity of these adverse effects and the variation thereof between patients will be described descriptively.

For the second aim of the project, we aim to pool this data across different treatment centres in order to increase power and obtain more quantitative information about possible characteristics of responders vs non-responders.

8.3 Other study parameters

The DM-TRD will be used as a continuous variable in regression and mixed model analyses. For illustrative purposes the scores of this scale can be split into tertiles (low medium and high levels of TRD).

PIT and clinical data will be combined and used to (iteratively) train machine learning algorithms, to build an optimal prediction tool for clinical decision-making: Therefore, we adopt a computational psychiatry approach, a rising field fueled by the lack of breakthroughs in psychiatric practice and inspired by advances in cognitive neuroscience and data-science. Computational psychiatry aims to improve clinical practice through mechanism- and machine-learning based predictions. Accordingly, we will use advances in computational cognitive neuroscience (PIT) and machine-learning (prediction) towards improved outcomes for TRD patients. This is timely because of evidence of clinical predictive value of PIT (Huys, 2016, Chen 2020), iSk registration for TRD and the availability of solid computational frameworks with readily employable machine-learning

algorithms, which enable us to perform predictions on the individual level within high-dimensional data.

Following the STROBE22 guideline, we will build a model to predict response in terms of depressive symptom reduction after 4 weeks of treatment with esketamine intranasal sprays. Clinical and computational parameters from PIT (easy to administer, web-based test measuring the influence of affect on reward-driven behaviors), collected before treatment initiation in 350 TRD patients, will be used as predictors. To predict response based on multiple predictors (PIT, questionnaire, demographical, clinical data) I will follow TRIPOD(-AI) guidelines and use common machine learning procedures (i.a. support vector machine, penalized regression and tree-based approaches) with cross-validation to prevent overfitting. The best algorithm in terms of precision-recall area under the curve will be tested on a hold-out test dataset (not involved in algorithm tuning) against at least reasonable specificity (90%) for non-response, making it acceptable for clinical purposes. As external validity is very important (and often not taken into account) in translational research, we will test algorithms again through continuous data collection and assess clinical utility with common test-statistics. Test data will be used to optimize algorithms iteratively, by further hyperparameter tuning (test and tune procedure).

For each separate analysis done in this consortium, we will pre-register an analysis plan at the Open Science Framework (<https://osf.io/>)

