Since December 18th 2019, esketamine intranasal obtained a European marketing authorization from EMEA. Thereafter, the manufacturer issued a compassionate use program (CUP) for the Netherlands before the reimbursement would be established, aiming at severely treatment resistant depressed patients (e.g. unsuccessful response to MAO-Inhibitors and/or ECT). As treatment with esketamine intranasal requires protocolized administration under strict supervision of patients in at least a day-care treatment facility, a limited number of centres will provide esketamine treatment, initially via the CUP, which, after reimbursement, was continued with new treatment centres. Current centres where esketamine intranasal spray treatments are administered: Radboudumc, Amsterdam UMC, UMC Utrecht, LUMC, GGZ Drenthe, ApareeGGZ, UMCG, Elisabeth Tweesteden Ziekenhuis, Maxima Medisch Centrum Eindhoven, Mondriaan / PsyQ Maastricht, GGZ Delfland, Antonius

ziekenhuis Nieuwegein, Parnassia Psy-Q Den Haag, Parnassia Antes, Parnassia Noord-Holland Castricum, Synaeda/GGZ Friesland, Vincent van Gogh, ProPersona, GGNet, GGZ Centraal, Reinier v Arkel, Amphia, Emergis, Rivierduinen, GGZ Noord-Holland Noord, Lentis, Spaarne gasthuis, Altrecht, Isala, Rivierenland, Ziekenhuis Groep Twente, Gelre Ziekenhuis, GGZ InGeest. These centres are collaborating on exchanging treatment protocols and clinical experience in order to increase the knowledge with this new application.

OBJECTIVES

Primary Objective: To collect pseudo-anonymized short- and long-term effectiveness and acceptability data for the treatment with esketamine intranasal in treatment resistant depressed patients treated in collaborating esketamine treatment centres in the Netherlands.

Secondary Objective(s):

[figure not shown]
To pool pseudoanonymised data of effectiveness and acceptability of esketamine intranasal from based on clinical registrations in patient's real-world health records.

To use predicted treatment response based on pooled clinical and behavioural data as pre-selection tool.

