2.4 Sample size calculation

As this is a cohort study, in which we want to use clinical data for summary purposes regarding effectiveness and acceptability, we did not perform an a priori power calculation.

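### Section 8.3 treats 90% specificity for non-response as clinical acceptability, but a rule with no predictive value can meet that criterion

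*Protocol*

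**What the plan says.** The third objective, in the Summary and the Objectives, gives the intended use: "To use predicted treatment response based on pooled clinical and behavioural data as pre-selection tool". Section 8.3 describes the model: "we will build a model to predict response in terms of depressive symptom reduction after 4 weeks of treatment with esketamine intranasal sprays". Its predictors are clinical and PIT-task data "collected before treatment initiation in 350 TRD patients".

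Several algorithms are trained with cross-validation. The one with the best precision-recall AUC goes to a hold-out set kept out of tuning, where it is judged "against at least reasonable specificity (90%) for non-response, making it acceptable for clinical purposes". This is the only numerical pass mark for the model in the protocol. No minimum precision-recall AUC, sensitivity or predictive value stands beside it.

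Section 8.3 also promises further checks: "we will test algorithms again through continuous data collection and assess clinical utility with common test-statistics". It cites TRIPOD(-AI) and commits to a pre-registered analysis plan for each analysis. It does not state the response cut-off, the size of the hold-out, or whether the hold-out is part of the 350. On sample size, section 2.4 says "we did not perform an a priori power calculation".

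**The concern.** The sentence in 8.3 is a decision rule with a clinical conclusion attached. Specificity can be set to any value by moving the cut-off, whatever the quality of the model. Only together with sensitivity or predictive value does it show that flagged patients differ from the rest. A tool for pre-selection could therefore be called acceptable when the patients it flags do no worse than average, or when many of them would have responded.

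A second, smaller matter is the wording. The model is said to predict response, while specificity is stated for non-response. The positive class is never named, and 90% protects a different group depending on which it is.

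**Working it through.** **Inputs from the protocol (8.3):** specificity threshold 90%; 350 patients. Neither figure is derived in the protocol, so there is no calculation to reproduce.

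**Inputs assumed, because the protocol gives none:** AUC 0.50 to 0.70 with a binormal, equal-variance score; non-response rate 50%, varied from 30% to 70%; hold-out of 20-30% of 350; relevant outcome class 30-60% of the hold-out.

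**1. A rule with no information.** Take non-response as the positive class and flag a random fraction f.
- Specificity = 1 - f and sensitivity = f.
- PPV = f·p / [f·p + f·(1 - p)] = p, where p is the non-response rate.
- With f = 0.10: specificity 90%, sensitivity 10%, PPV = p.
- With f = 0: specificity 100%, sensitivity 0%.

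Both rules meet the 90% figure.

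**2. A model with moderate discrimination.** Sensitivity at 90% specificity = Φ(√2·Φ⁻¹(AUC) - 1.2816).
- AUC 0.50: 10%.
- AUC 0.65: 23%.
- AUC 0.70: Φ(1.4142 × 0.5244 - 1.2816) = Φ(-0.540) = 29.5%.

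PPV at AUC 0.70 and p = 0.50 is 0.50 × 0.295 / (0.50 × 0.295 + 0.50 × 0.10) = 0.747, about 75%. One in four flagged patients would have responded. The same formula gives a PPV of 56% at p = 0.30 and 87% at p = 0.70.

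**3. The positive class.**
- Non-response positive: at most 10% of responders are wrongly flagged.
- Response positive: 90% of non-responders must be flagged. At AUC 0.70, 100% - 29.5% = 70.5% of responders are then flagged too.

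**4. Precision (secondary, resting on the assumed sizes).** Only one outcome class enters the denominator.
- Smallest: 0.20 × 350 × 0.30 = 21.
- Largest: 0.30 × 350 × 0.60 = 63.

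Exact (Clopper-Pearson) 95% CIs at the smallest count that reaches 90%:

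| Count | Observed | 95% CI |
|---|---|---|
| 19/21 | 0.905 | 0.70-0.99 |
| 32/35 | 0.914 | 0.77-0.98 |
| 47/52 | 0.904 | 0.79-0.97 |
| 57/63 | 0.905 | 0.80-0.96 |

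**The case against.** **Precision-recall AUC comes first.** It depends on precision and recall, so a random rule would go forward only if no trained algorithm carried signal. This makes the extreme case less likely. But the ranking has no floor, so the best of a weak set still goes forward to a test that does not measure discrimination.

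**Later steps may cover it.** Renewed testing, TRIPOD(-AI) and the pre-registered plan could supply the missing measures. Hold-out size, interval method and class coding can properly sit in that plan, and their absence here is no error. None of these steps, as described, sets a companion criterion or withdraws the statement about clinical acceptability.

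**The positive class is fairly clear.** Specificity for non-response most naturally means that non-response is the positive class. That is accepted; the point is one of clarification.

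**Readings that go too far.** A reader might infer that 90% specificity cannot be verified with 350 patients. The protocol does not support this: it states neither the hold-out size nor that the hold-out comes from the 350. With a 50% hold-out and a true specificity of 98%, the power to place the lower 95% limit at or above 90% is 35-96%, for class shares of 30-70%. Later data could add precision.

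A reader might also infer that the test is a coin toss because a model with a true 90% often fails it. A true value equal to the cut-off fails about half the time at any sample size, so this says nothing about 350. A model with a true 95% fails only about 4-10% of the time at denominators of 21, 35, 52 and 63.

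**Conclusion.** The criterion is wrong as written. Under 8.3 a model with no predictive value can meet the stated condition for clinical acceptability, and this follows from the definition of specificity without any assumption. How much a model with some skill falls short depends on assumed inputs: about 29% sensitivity and 75% PPV at AUC 0.70 and 50% non-response, with PPV from 56% to 87% as non-response runs from 30% to 70%.

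Naming the positive class is a needed clarification, since the less natural reading protects the opposite group. Imprecision of the point estimate is a secondary point that holds only for the assumed 20-30% hold-out. The issue concerns the prediction objective, not the primary MADRS endpoint.

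**What to change.** In section 8.3, and in the pre-registered plan for the prediction analysis:

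- State that non-response is the positive class and that specificity is the share of responders not flagged.
- Fix the cut-off in the training data before the hold-out is opened.
- Report specificity, sensitivity, PPV and NPV in the hold-out with 95% CIs.
- Besides 90% specificity, require evidence of predictive value, for example a lower 95% bound of PPV for non-response above the cohort's non-response rate.
- Replace the claim of clinical acceptability with a statement that the model is a candidate for prospective validation.

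The cost is wording, slightly more analysis and a less favourable claim. The example criterion is demanding in a small hold-out. Take AUC 0.70 and 50% non-response. A hold-out of 105 would flag about 52 × 0.295 ≈ 15 non-responders and 53 × 0.10 ≈ 5 responders; 15/20 has an exact 95% CI of 0.51-0.91, just above 0.50. A hold-out of 70 would give about 10/14, with a CI of 0.42-0.92, and would not pass. The hold-out size should be chosen with this in mind.

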10. ADMINISTRATIVE ASPECTS, MONITORING AND PUBLICATION

10.1 Handling and storage of data and documents

All data (questionnaires and evaluations) will be primarily recorded in the patient's health record. Only after informed consent data will be abstracted and anonymised by a study-number. For the second aim of this project the study-number will only disclose the treating hospital where the patient was treated, no referral to initials or birth-date of participants will be made in the study-number. The key between the study-number and the patient will be stored at the hospital (at a secured directory only accessible to the local physician) and will not be shared outside the hospital.

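### The step offered for external validity is repeat testing on continuing data from the pooled cohort; no test of the 90% specificity threshold in a centre outside the training data is specified or guaranteed

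*Protocol*

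**What the plan says.** The third objective in the protocol Summary is to use predicted treatment response as a pre-selection tool. Section 8.3 sets out how the tool is to be built and tested:

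- **Development data.** Clinical and PIT parameters, "collected before treatment initiation in 350 TRD patients, will be used as predictors".
- **First test.** The best algorithm "will be tested on a hold-out test dataset (not involved in algorithm tuning"). The target is set "against at least reasonable specificity (90%) for non-response, making it acceptable for clinical purposes". Whether the hold-out is drawn by patient, by calendar time or by centre is not stated.
- **Step for external validity.** "As external validity is very important (and often not taken into account) in translational research, we will test algorithms again through continuous data collection".
- **What then happens to test data.** "Test data will be used to optimize algorithms iteratively, by further hyperparameter tuning (test and tune procedure").

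Section 8.2 describes the centre structure only as pooling: "we aim to pool this data across different treatment centres in order to increase power"; section 8.1 says the same. Under section 9.2, patients come from the referral centre or other participating centres. The Introduction lists the centres, says of them "These centres are collaborating on exchanging treatment protocols and clinical experience", and notes that new centres joined after reimbursement. Section 10.1 says that "the study-number will only disclose the treating hospital where the patient was treated", so the centre can be identified in the pooled data.

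**The concern.** Section 8.3 names external validity as its goal, but the method it gives is more data from the same consortium. Unless the split follows centre, repeat testing of this kind is temporal validation: it asks whether the model holds in later patients. It does not ask whether the model holds where it was not trained.

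The protocol gives reasons to expect some differences between centres. The outcome is a clinician-rated MADRS (section 6.1.1). Diagnosis may rest on a clinical or a semi-structured interview (section 6.3). The background antidepressant may be optimised (section 3.2), and the session dose varies (section 3.1). The listed sites include university hospitals, general hospitals and mental health institutions.

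The tool is meant to inform patient selection, and the 90% threshold is what section 8.3 says makes it clinically acceptable. Specificity at a fixed cut-off is sensitive to a shift in the score distribution, even where the ranking of patients is unaffected. A report following the text could describe the model as externally validated without having tested it in an unseen centre.

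**Working it through.** There is no protocol figure to reproduce: section 2.4 says no power calculation was done, 350 has no derivation, and 90% is a threshold rather than a result. The main check is on the text; the arithmetic only illustrates scale.

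**1. Does any step secure a test in an unseen centre?**

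| Step in section 8.3 | Separated from training by | Centre named or reserved? |
|---|---|---|
| Cross-validation | not stated | no |
| Hold-out test | not used in tuning; unit of split not stated | no |
| Repeat test on continuing data | time, by implication | no |
| Reuse of test data | nothing; the data enter tuning | no |

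None does. The last row also affects the third. Once test data have tuned the model, they are no longer independent of it, so even the temporal check holds only if each revised model is tested on data not yet used.

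**2. Patients per centre.** The Introduction lists 33 centres (counted). If the 350 were spread evenly, 350/33 = 10.6 per centre. If 30-70% of these fall in the class that specificity counts (assumed), that is 10.6 × 0.3 = 3.2 to 10.6 × 0.7 = 7.4 patients per centre, too few to judge a single centre.

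**3. Specificity under a centre shift (assumed).** Take scores in the class that specificity counts as normal, with a common cut-off giving 90%, so the cut-off is z = 1.2816. If a centre's scores are shifted by d SD, its specificity is Φ(1.2816 − d) for an upward shift and Φ(1.2816 + d) for a downward one.

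- d = 0.3: Φ(0.9816) = 0.837; Φ(1.5816) = 0.943
- d = 0.5: Φ(0.7816) = 0.783; Φ(1.7816) = 0.963

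**4. Second model (assumed).** Let centre specificity vary on the logit scale with between-centre SD τ around logit(0.90) = ln 9. The 95% range for a centre is expit(ln 9 ± 1.96τ):

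| τ | 95% range |
|---|---|
| 0.2 | 86-93% |
| 0.4 | 80-95% |
| 0.6 | 74-97% |
| 0.8 | 65-98% |

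**5. Precision of the pooled figure.** With 20-30% of the 350 held out and 30-70% of those in the counted class (both assumed), n runs from 350 × 0.2 × 0.3 = 21 to 350 × 0.3 × 0.7 = 73.5, about 74. The Wilson 95% interval around an observed 90% runs from 70-97% at the smallest n to 81-95% at the largest. Sampling error alone is therefore wide, and a difference between centres would come on top of it.

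**The case against.** **The protocol defers to plans not shown.** Section 8.3 commits to TRIPOD(-AI) and to a pre-registered plan for each analysis. The unit of the split may be set there, so its absence from the protocol is not in itself an error. This stands. What remains is that the protocol itself pairs the goal of external validity with a method that does not secure it.

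**Temporal validation has value.** It is a recognised, if weaker, external check. This stands too; the gap concerns transport to new centres.

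**Centres may be alike.** They exchange treatment protocols and treat to one manufacturer guideline, which would tend to reduce differences. This is fair: the size of the variation is unknown, and the shifts and τ above are assumptions. They also describe spread among any centres, training centres included, so they do not measure a penalty specific to new ones.

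**Stronger readings that a reader might infer, and that the protocol does not support:**

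- *That the repeat test covers only later patients in the same centres.* Section 8.3 does not say which centres supply the continuing data, and the Introduction says new centres joined, so unseen centres may be included by chance.
- *That the protocol claims 90% specificity.* It sets 90% as a threshold and reports no performance.
- *That local habits in the Continuation Phase could distort the result.* The predicted outcome is at 4 weeks, and that phase starts in week 5.
- *That discrimination must fall in new centres.* Centre is not among the listed predictors. If centres differ only in their overall response level, a model without centre terms need not rank patients worse in a new one.

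**Conclusion.** The point holds in a limited form. Section 8.3 offers repeat testing on continuing data as its step for external validity, separates no data by centre, and returns test data to tuning. Following the text secures no test of the 90% threshold in a centre that supplied no training data. Such a test could occur by accident of accrual, and an unseen analysis plan could require it.

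How far specificity would move cannot be derived from the protocol. If score distributions shift by 0.3 to 0.5 SD between centres, 90% overall corresponds to about 78-84% or 94-96% in a shifted centre; under the logit model with τ of 0.4 to 0.6, the 95% range is 80-95% to 74-97%. Prediction is a secondary objective, so this does not touch the MADRS analysis. It is still worth correcting, because the tool is intended for clinical selection and the repair uses data already in hand.

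**What to change.** 1. In section 8.3, describe the repeat test on continuing data as temporal validation.
2. Add one centre-based test, using the hospital code in the study number:
   - internal-external cross-validation, leaving out one group of centres at a time with all tuning done on the remainder; or
   - a locked model tested in whole reserved centres, for example those joining after lock, that are never used for tuning.
3. State that any data used for tuning no longer count as test data, and that each revised model is tested on data not yet used.
4. Report specificity, sensitivity and calibration by centre group, with their spread.

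**Cost.** A change of wording, a grouped split and some extra analysis; no new data, visits or staff. Single-centre estimates would be too imprecise at about 10.6 patients per listed centre, so centres must be grouped: six groups, for example, would average 350/6 = 58 patients each. Estimates by group would still be imprecise, and the reported performance may be less favourable.
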